1.2. Schema

1.3. Schedule of Activities (SoA)

	Screening	IMP Treatment Period				In-patient Stay ¹⁾	Follow-up Period ²⁾			Unscheduled ³⁾
Visit	V1	V2	V3-15 ^{1,4)}	V16 ⁴⁾	EWD ⁵⁾	V17-29	V30	V31	V32	UV
Day (Visit window)	Up to 48h prior to V2	Day 1	Days 2-14	Day 15 (+1 day)		Days 16-28	Day 22 (±1 days)	Day 29 (±1 days)	Day 60 (±3 days)	
Eligibility/General										
Informed consent	X									
Eligibility criteria	X	x ⁶⁾								
Demographics	X									
Medical history	X									
IMP and Concomitant Therapy										
Randomization		x								
IMP administration ⁷⁾		x	x							(x)
Check of fasting criteria		x	x							(x)
IMP accountability			x ⁸⁾	x	x					
Previous and concomitant therapy	X	x	x	x	x	x	x	x		(x)
Trial Assessments and Procedures										
8-point ordinal scale	X	x	x	x	x	x	x	x	x	(x)
Supplemental O ₂	X	x	x	x	x	x	x	x	x	(x)
Oxygen saturation	X	x	x	x	x	x				(x)
Hospitalization	X	x	x	x	x	x	x	x	x	(x)
Physical examination	X			x	x					(x)
Body weight and height	X									
Vital signs	X	x	x	x	x	x				(x)
12-lead ECG ⁹⁾	X									(x)
Adverse events	X	x	x	x	x	x	x	x	x ¹⁰⁾	x
Biochemistry ¹¹⁾	X	x ¹²⁾	Days 3, 5, 8, 11 (all ± 1 day)	x	x					(x)
Haematology ¹¹⁾	X	x ¹²⁾	Days 3, 5, 8, 11 (all ± 1 day)	x	x					(x)
Urinanalysis ¹¹⁾	X	x ¹²⁾		x	x					(x)
Pregnancy testing ¹³⁾	X			x	x					(x)
Oropharyngeal swab		x								
Pharmacokinetics ¹⁴⁾		x								
Blood sample for future exploratory analysis		x ¹²⁾		x	x					

1. Daily visits until discharge. Visits will be re-initiated in case of a COVID-19 related hospital re-admission.
2. Follow-up visits by phone or video.
3. Assessments marked with () will be performed per investigator judgment at e.g., COVID-19 related hospital re-admission after Day 29.
4. Days 8 and 15 visits must be performed for all subjects. If a subject is discharged before Day 8, the Day 8 visit will be done by phone or video. Site assessments e.g., oxygen saturation, vital signs and blood sampling will not be performed.
5. An early withdrawal (EWD) visit should be performed for subjects withdrawn from the trial prior to Day 15 (Visit 16).
6. Re-evaluation of eligibility including evaluation of electrocardiogram (ECG) and laboratory results from screening.
7. IMP is administered b.i.d. from Days 1 to 14.
8. IMP accountability will be performed at hospital discharge.
9. A historical 12-lead ECG is acceptable. The ECG should be ≤2 days old at the time of screening (Visit 1).
10. SAEs only.

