6.1. Investigational Medicinal Product Administered

Each subject will be randomized to receive treatment with the IMP (C21 or placebo). The IMP will be administered as a capsule for oral administration. Each subject will receive 4 capsules per day, divided in 2 doses given twice a day.

IMP will be administered in fasting conditions (see Section 5.3). C21 is an AT2R agonist. The drug substance is 3-[4-(1H-imidazol-1-ylmethyl)phenyl]-5-(2-methylpropyl)thiophene-2-[(N-butyloxylcarbamate)-sulphonamide] sodium salt supplied as a free form equivalent (eq.) 50 mg C21 oral capsule.

Table 1. Investigational Medicinal Product Administered

IMP Name	Active / C21	Placebo
Dose Formulation	Capsule	Capsule
Unit Dose Strength(s)	52.3 mg pr capsule	Placebo
Dosage Level(s)	2 capsules, b.i.d.	2 capsules, b.i.d.
Excipients	Mannitol, Anhydrous colloidal silica, Magnesium stearate	Mannitol, Anhydrous colloidal silica, Magnesium stearate
Capsule	Vcaps® plus	Vcaps® plus
Route of Administration	Oral	Oral
Dosage description	Subjects will receive 100 mg C21 b.i.d. on Day 1 to Day 14.	Subjects will receive Placebo b.i.d. on Day 1 to Day 14.
Sourcing	Provided centrally by the sponsor	Provided centrally by the sponsor
Packaging and Labeling	IMP will be provided in a container. Each container will be labeled as required per country requirement.	IMP will be provided in a container. Each container will be labeled as required per country requirement.

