7.1. Discontinuation of Investigational Medicinal Product

A subject should be withdrawn from the IMP treatment if it in the opinion of the investigator is medically necessary or if it is the wish of the subject.

If IMP treatment is discontinued, the date of last IMP administration and the date and reason for treatment withdrawal should be reported in the eCRF. If a subject is removed from treatment because of an AE, the reason for treatment withdrawal should always be stated as 'adverse event' irrespective of whether this was the investigator's or the subject's decision.

If IMP treatment is discontinued, the investigator should make all efforts to ensure that the subject will remain in the trial and ensure that the subject attends the remaining visits in the trial.

IMP treatment should be discontinued in case of drug induced liver injury according to criteria specified in FDA guidance ([FDA, 2009](#)), moderate or severe impairment of hepatic function (e.g., Child-Pugh class B or C where alterations in the score components are not due to another underlying disease (see Section 8.4.5)), or severe renal impairment (i.e., estimated glomerular filtration rate (eGFR) ≤ 30 ml/min/1.73 m²).

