12.3 Treatments

12.3.1 Extent of Trial Drug Exposure

For the IMP, summary statistics will be provided for SS for duration of exposure, total number of dose administrated and total cumulative dose in the treatment period. The number and percentage of subjects who experience at least one overdose on any day during the treatment period will be provided. Any dose of C21 exceeding a total daily dose of 200 mg (i.e., 4 capsules of IMP) is considered an overdose.

The total cumulative dose will be calculated as:

Cumulative dose (mg) = 50x (Number of Capsules dispensed [56] – Capsules returned)

The total number of doses administered will be the difference between the number of capsules dispensed [56] and number of capsules returned. If returned amount is missing and the subject is indicated to have completed treatment, they will be treated as taking all capsules. If the subject discontinues treatment and

returned amount is missing, they will be treated as taking capsules as planned up to the day of discontinuation derived as:

$$\text{Cumulative dose (mg)} = 50 * (4 * (\text{duration of exposure}))$$

where duration of exposure for this calculation will be set to a minimum of duration of exposure and 14 days.

If first dose for subject that discontinues treatment and has no returned amount is in the evening (p.m.) the calculation will be as follows:

$$\text{Cumulative dose (mg)} = 50 * (2 + 4 * (\text{duration of treatment} - 1))$$

For these subjects with first dose in the p.m., if duration of exposure is >14 indicating the subject took the full treatment course, the cumulative dose will be assumed to be 56.

The duration of exposure will be derived as:

$$\text{Duration} = (\text{Last dose of IMP} - \text{First dose of IMP}) + 1$$

Duration of exposure will be summarized overall, by subjects whose first dose was in the morning and by subjects whose first dose was an evening dose. Duration of exposure will also be summarized by duration categories, the number of subjects exposed for 1-6 days, 7-13 days and 14+ days.

Overall compliance will be calculated as follows:

$$\text{Treatment Compliance (\%)} = 100 * \frac{\text{Total Number of Doses administered}}{\text{Expected Number of Capsules}}$$

For subjects who completed treatment, expected number of capsules will be 56. For subjects who discontinue treatment:

$$\text{Expected Number of Capsules} = 4 * \text{Duration of exposure}$$

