Compliance will be summarized using the following categories: <80%, 80-90%, >90%.

The percentage of doses taken in hospital will be presented and derived as follows:

$$\% \text{ of Doses taken} = 100 * \frac{56 - \text{Number of Capsules dispensed on discharge}}{\text{Cumulative dose (total capsules taken)}}$$

For subjects who do not discharge during the treatment period or who discontinue the study prior to discharge from hospital during the treatment period, the % doses taken will be 100%.

The number of doses missed and reason dose missed will be summarized for subjects (this information will only be collected during the hospitalized period). Trial drug exposure will be listed. Drug accountability will also be listed.

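### The SAP's percentage of doses taken in hospital can exceed 100% for subjects who stop IMP in hospital, stay in the trial and go home within the treatment period, and its dose count is a capsule count

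*SAP*

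**What the plan says.** All the exposure rules are in SAP 12.3.1.

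- **Percentage in hospital.** The numerator is 56 less the "Number of Capsules dispensed on discharge". The denominator is labelled "Cumulative dose (total capsules taken", with the bracket closed after it. The result is set to 100% under one exception: "For subjects who do not discharge during the treatment period or who discontinue the study prior to discharge from hospital during the treatment period".
- **Dose count.** "The total number of doses administered will be the difference between the number of capsules dispensed [56] and number of capsules returned".
- **Cumulative dose.** "Cumulative dose (mg) = 50x (Number of Capsules dispensed [56] – Capsules returned"), which is a quantity in mg. Further down, for subjects who stop treatment with no return count, had an evening first dose and have more than 14 days of exposure, cumulative dose is set to 56.
- **Compliance.** The dose count above is divided by the expected number of capsules.

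Protocol 6.1 gives the unit of a dose: "Each subject will receive 4 capsules per day, divided in 2 doses given twice a day". The schedule of activities gives the course length: "IMP is administered b.i.d. from Days 1 to 14". On stopping IMP, Protocol 7.1 says that "the investigator should make all efforts to ensure that the subject will remain in the trial".

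**The concern.** The numerator treats every capsule not sent home as taken in hospital, while the denominator counts only capsules actually taken. The two are consistent only if every capsule held back at discharge was in fact swallowed.

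The 100% exception turns on leaving the study, not on stopping IMP. The documents expect these to differ: Protocol 7.1 lists reasons to stop IMP and asks sites to keep such subjects in the trial, and SAP 12.1 plans to tabulate those who stop treatment yet complete the trial. A subject in that group who goes home within the treatment period falls through to the formula, and capsules never taken are counted as taken in hospital.

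The SAP gives no purpose for this percentage. A natural one is to show how much dosing was supervised. Protocol 2.3.1 reports markedly lower C21 exposure with food, and Protocol 6.4 has staff document fasting during the stay, whereas home dosing is assessed at Day 15. Values above 100% would spoil that description.

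The dose count is a separate labelling error: a reader of the table would take 56 doses to mean 56 dosing occasions.

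**Working it through.** **Inputs**

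- 4 capsules a day in 2 doses, so 2 capsules per dose (Protocol 6.1).
- 14 days, twice daily (Protocol 1.3).
- 50 mg per capsule and 56 capsules dispensed (SAP 12.3.1).
- Capsules recorded as dispensed on discharge for a subject already off IMP: not given in either document. Protocol 6.2 covers only subjects who take remaining IMP home. The main case below assumes 0; the range runs up to all leftover capsules.

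**The plan's own figure.** 4 × 14 = 56 capsules, as the SAP states. That is 2 × 14 = 28 doses and 50 × 56 = 2800 mg.

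**Percentage in hospital.** Let IMP stop at the end of Day k after a morning first dose, so 4k capsules are taken, all in hospital. Let d be the capsules recorded as dispensed on discharge, with discharge by Day 14. The SAP value is 100 × (56 − d) / 4k; the true value is 100%.

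| IMP stops after | Capsules taken | d = 0 | d = all leftover (56 − 4k) |
|---|---|---|---|
| Day 3 | 12 | 100 × 56/12 = 467% | 100% |
| Day 5 | 20 | 100 × 56/20 = 280% | 100% |
| Day 7 | 28 | 100 × 56/28 = 200% | 100% |
| Day 10 | 40 | 100 × 56/40 = 140% | 100% |
| Day 13 | 52 | 100 × 56/52 = 108% | 100% |

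The formula is sensible elsewhere. A completer discharged after Day 7 with 28 capsules gets 100 × (56 − 28)/56 = 50%. A subject discharged after Day 7 with 28 capsules who stops at home after Day 10 gets 100 × (56 − 28)/40 = 70%.

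**Dose count.** A full course is reported as 56 − 0 = 56 doses, against 56/2 = 28. A stop after Day 5 is reported as 20, against 10.

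**Compliance.** For a stop after Day 5 it is 100 × 20/(4 × 5) = 100%, capsules over capsules, which is correct. If the dose count were halved and fed into the same formula, it would become 100 × 10/20 = 50%.

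**Units of cumulative dose.** The special case set to 56 should read 50 × 56 = 2800 in mg. In the percentage formula, cumulative dose is used as a capsule count. Taken literally in mg, a stop after Day 5 with d = 0 would give 100 × 56/(50 × 20) = 5.6%.

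**The case against.** The strongest reply is that the high percentages rest on a field whose content is unknown. If sites record the leftover capsules as dispensed on discharge, every affected subject gets exactly 100%; if the field is blank, the result is missing. The CRF is not available here. This stands, and 280% is therefore a conditional figure. It does not rescue the rule, because the SAP does not state the recording convention its formula would need.

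A second reply is that few subjects qualify. All three conditions are needed: IMP stopped in hospital, subject still in the trial, and discharge within the treatment period. This also stands. A reader might infer that everyone who stops IMP before discharge is affected. The exception rules that out for those still in hospital when the treatment period ends and for those who leave the study before discharge. Nor do the documents say how many subjects would qualify, so no shift in an arm mean can be claimed.

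Third, the SAP openly defines its dose count in capsules, and both compliance and the main mg formula are right. So the dose count is a matter of labelling, though one that doubles a reported number. A reader might also infer that it can never be squared with the count of missed doses. That comparison works only for subjects hospitalised throughout treatment, because missed doses are collected only in hospital.

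Finally, no planned analysis uses the in-hospital percentage, and exposure and accountability are listed by subject, so an impossible value would be noticed. That limits the harm without making the rule correct.

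**Conclusion.** Both rules are wrong as written, and both are minor.

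1. The percentage formula exceeds 100% for the three-condition group whenever fewer capsules are recorded as dispensed on discharge than were left over. With 0 recorded, the results for stops after Day 3 to Day 13 run from 467% down to 108%. The size depends on that assumption and on the day of stopping.
2. The reported number of doses is exactly twice the true number. This needs no assumption.

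The mixing of mg and capsules under the name cumulative dose is a related slip in the same section.

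A reader might infer that compliance, the per-protocol set or the efficacy results are compromised. The documents do not support that. Compliance is capsules over capsules, and the per-protocol exclusions in SAP 9.5.3 do not use these quantities. No efficacy test, power figure or significance level changes.

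**What to change.** - **Percentage in hospital.** Preferably define the numerator as capsules taken in hospital, from the Exposure – Dose Administration page, over total capsules taken. This no longer depends on what is recorded as dispensed on discharge. If that page does not support a capsule count, extend the 100% rule to subjects who permanently discontinue IMP before discharge. Do not base that rule on the last-dose date falling on or before the discharge date: a subject who leaves in the morning and takes a dose at home that evening would be misclassified.
- **Dose count.** Relabel it as capsules administered, or divide by 2 to report doses. In either case keep the compliance numerator in capsules.
- **Cumulative dose.** Replace 56 by 2800 mg in the evening-first-dose rule, and name the denominator of the percentage as capsules taken.

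The cost is a few sentences of SAP text and a few lines of programming before database lock. SAP 10.3 already draws dosing dates from the Exposure page, so no new collection should be needed once its content has been checked.

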12.3.2 Prior and Concomitant Therapies

Therapies received prior and concomitantly with IMP, categorized by medication group and subgroup according to the World Health Organization Drug Dictionary (WHODRUG) Global version March 2021 B3 or later will be summarized using ITT.

Prior and concomitant therapies (see Section 10.5) will be summarized separately using Anatomical Therapeutic Chemical (ATC) levels 2 and 4. The number and percentage of subjects using any therapy will be displayed together with the number and percentage of subjects using at least one therapy within each medication group and subgroup.

A summary of vaccinations will be provided for the ITT. Vaccinations will be collected on the concomitant medication page and will be identified via code review by medics.

12.4 Important Protocol Deviations

Per PRA/ICON processes, protocol deviations data will be entered into the PRA/ICON system of record (PSO), in accordance with the Protocol Deviation Guidance Document. Important protocol deviations are defined in the protocol deviation guidance document. The last approved version of protocol deviation guidance will be finalized before the database lock. The trial team and the Sponsor will conduct on-going reviews of the deviation data from PSO and the resulting set of evaluable subjects throughout the trial, adjusting the deviation criteria as seems appropriate.

Protocol deviation data will be reviewed prior to database lock and important deviations with an impact on efficacy leading to the elimination of subjects from the PP will be identified. The PP must be finalized at the blinded data review meeting (or earlier), prior to database lock.

The number of subjects with Important protocol deviations will be summarized in the ITT by category of violation and by treatment group including subset of Important protocol deviations leading to exclusion from the PP. Site level protocol deviations will be summarized as individual subject level protocol deviations for subjects at the impacted site. All protocol deviations will also be listed using the ITT.

12.5 Efficacy Analysis

12.5.1 Hypothesis Testing Strategy

The objective of the primary efficacy analysis will be to evaluate the efficacy of C21 versus placebo as add on to SoC in subjects with COVID-19 by comparing the all-cause mortality at Day 60. The aim of the efficacy analysis is to demonstrate superiority of C21 over placebo.

The null and alternative hypotheses used to evaluate the efficacy for the primary endpoint are to evaluate the difference in time to all-cause mortality up to study follow-up Day 60 between C21 ($S_1(t)$, survival distribution for C21 over time t) and placebo ($S_2(t)$, survival distribution for placebo over time t).

Null hypothesis i.e. no difference in survival up to Day 60 between the two groups:

$$H_0: S_1(t) = S_2(t)$$

Alternative hypothesis i.e. difference in survival up to Day 60 between the two groups :

$$H_1: S_1(t) \neq S_2(t)$$

The overall 2-sided significance level of 5% will be applied to the primary endpoint and the 2-sided p-value obtained from a log-rank test presented in the outputs.

Analysis of the key secondary endpoints will be performed using a hierarchical testing procedure as defined in Section 12.0. All tests for the key and non-key secondary endpoints will be at the 2-sided significance level of 5% and testing the null hypotheses that there is no difference between C21 and placebo, against the alternative hypothesis that C21 is better than placebo. Efficacy of C21 in comparison to Placebo with respect to the key secondary endpoints will be demonstrated only if efficacy is demonstrated in the primary endpoint otherwise these endpoints will be exploratory only.

12.5.2 Primary Estimand

The estimand of interest is all-cause mortality up to Day 60 defined as the time to day of death from any cause assessed for the intention-to-treat population with treatment as randomized, independent of treatment withdrawal or important protocol deviations according to the treatment policy, with subjects with no confirmed death before or at Day 60 being censored at day of withdrawal/Day 60 follow-up (refer to Appendix 1).

Intercurrent events will be handled according to the treatment policy strategy. Treatment policy strategy is defined as the strategy that considers "The occurrence of the intercurrent event is irrelevant: the value for the variable of interest is used regardless of whether or not the intercurrent event occurs" (See ICH E9 R1 addendum). All scheduled scores of clinical status will be considered for the analysis, even if collected after the occurrence of intercurrent events of (1) discontinuing IMP, (2) returning to initial treatment and/or (3) initiating a new treatment.

12.5.2.1 Imputation Methods

Missing data will not be imputed for the primary estimand.

12.5.2.2 Primary Analysis

All-cause mortality at Day 60 will be defined as time to day of death from any cause within Day 1 to Day 60 follow-up (refer to Section 10.11). All-cause mortality will be estimated using the Kaplan-Meier methodology where subjects in this analysis without the event will be censored at Day 60 follow-up. Withdrawn subjects without the event will be censored at day of discontinuation (this assumes the censoring is non-informative).

Treatment groups will be compared using a stratified log-rank test adjusting for treatment, actual baseline disease severity and region. The p-value from the stratified log-rank will be presented. The size of the treatment effect will be estimated as a hazard ratio, obtained using a Cox proportional hazards regression model, and the Cox regression model will include a factor for randomized treatment, baseline disease severity and region. The estimated Hazard Ratio comparing C21 to Placebo will be presented together with the corresponding 95% CI (based on Wald test). A Kaplan-Meier plot of time to all-cause mortality will also be produced.

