7.3. Lost to Follow up

A subject will be considered lost to follow-up if he/she repeatedly fails to return for scheduled visits and is unable to be contacted by the trial site.

The following actions must be taken if a subject fails to return to the clinic for a required trial visit:

- The site must attempt to contact the subject and reschedule the missed visit as soon as possible, counsel the subject on the importance of maintaining the assigned visit schedule and ascertain whether the subject wishes to and/or should continue in the trial.
- Before a subject is deemed lost to follow-up, the investigator or designee must make every effort to regain contact with the subject (where possible, 3 telephone calls, and if necessary, a certified letter to the subject's last known mailing address or local equivalent methods). These contact attempts should be documented in the subject's medical record.
- Should the subject continue to be unreachable, he/she will be considered to have withdrawn from the trial.

8. Trial Assessments and Procedures

- Trial procedures and their timing are summarized in the SoA. Protocol waivers or exemptions are not allowed.
- Immediate safety concerns should be discussed with the sponsor or designee immediately upon occurrence or awareness to determine if the subject should continue or discontinue IMP.
- Adherence to the trial design requirements, including those specified in the SoA, is essential and required for trial conduct.
- All screening evaluations must be completed and reviewed to confirm that potential subjects meet all eligibility criteria. The investigator will maintain a screening log to record details of all subjects screened and to confirm eligibility or record reasons for screening failure, as applicable.
- Procedures conducted as part of the subject's routine clinical management (e.g., PCR tests for SARS-CoV-2 collected less than 3 days prior to Visit 2 (or less than 7 days prior to Visit 2 in case of documented inability to obtain a repeat sample and progressive disease suggestive of ongoing SARS-CoV-2 infection)) and obtained before signing of the ICF may be utilized for screening or baseline purposes provided the procedures met the protocol-specified criteria and were performed within the timeframe defined in the SoA.

The maximum amount of blood collected from each subject over the duration of the trial, including any extra assessments that may be required, will not exceed 130 mL.

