8.5.1. Time Period and Frequency for Collecting AE and SAE Information

All AEs will be collected from signing of the ICF until Day 29 at the timepoints specified in the SoA (see Section 1.3). SAEs will further be collected until Day 60. All AEs are followed until they have reached a final outcome (see Section 10.2) or the subject's participation in the trial ends, whichever comes first.

All SAEs will be recorded and reported to the sponsor or designee immediately and under no circumstance should this exceed 24 hours after SAE awareness, as indicated in Appendix 2 (see Section 10.2). The investigator will submit any updated SAE data to the sponsor within 24 hours of it being available.

Information on SAEs must be entered in the eCRF.

Investigators are not obligated to actively seek information on AEs or SAEs after conclusion of the trial participation. However, if the investigator learns of any SAE, including a death, at any time after a subject has been discharged from the trial, and he/she considers the event to be reasonably related to the IMP or trial participation, the investigator must promptly notify the sponsor regardless of the time that has elapsed (post-trial events).

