9.5. Sample Size Determination

The sample size is based on the all-cause mortality up to Day 60. For the placebo (SOC) group, the proportion of subjects dead at Day 60 is estimated to 10% ([Marconi et al., 2021](#)).

With 150 evaluable subjects per trial group, there will be an 80% power to detect a difference between C21 and placebo if the proportion of subjects dead at Day 60 in the C21 group is 2.5% (corresponding to a HR of 0.24). In this calculation, a 5% withdrawal rate has been assumed. For the actual detection limit (corresponding to 50% power), if 15 subjects die in the placebo group, significance will be seen if at most 6 subjects die in the C21 group.

This assumes using a 2-sided test at a 5% significance level. Analysis will be by intention-to-treat; thus, all randomized subjects should be accounted for in the statistical evaluation.

10. Supporting Documentation and Operational Considerations

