8.1 Sample Size Considerations

The sample size is based on the all-cause mortality up to Day 60. For the placebo (SOC) group, the proportion of subjects dead at Day 60 is estimated to 10% (Marconi et al., 2021).

With 150 evaluable subjects per trial group, there will be an 80% power to detect a difference between C21 and placebo if the proportion of subjects dead at Day 60 in the C21 group is 2.5% (corresponding to a Hazard Ratio of 0.24). In this calculation a 5% withdrawal rate has been assumed. For the actual detection limit (corresponding to 50% power), if 15 subjects die in the placebo group, significance will be seen if at most 6 subjects die in the C21 group.

This assumes using a 2-sided test at a 5% significance level. Analysis will be by intention-to-treat; thus, all randomized subjects should be accounted for in the statistical evaluation.

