12.5.3.1 Missing data

Imputation of data due to intercurrent events (treatment discontinuation due to lack of efficacy, occurrence of important protocol deviation, rescue therapy) will not be performed. Subjects who die will have their missing data set as non-responders in the relevant analysis for all time points of interest following the date of death.

Subjects who discontinue the trial for reasons other than death will have their data multiply imputed as per Section 10.19.1. It is anticipated that missing data will be due to discharged subjects not returning for subsequent scheduled visits, or a worsening of clinical status such that the subject can no longer participate in the trial, or due to missing follow-up visits.

The missing data pattern for the adjusted 8-point ordinal scale will be summarized and a distribution plot will be used to represent the pattern of missing data for the adjusted 8-point ordinal scale showing the proportion of missing data each day per treatment group.

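### The mortality primary endpoint has no required vital-status follow-up after trial withdrawal; near the plan's 15 vs 6 detection limit, one unrecorded C21 death would change the conclusion

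*SAP*

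**What the plan says.** **Censoring.** SAP 12.5.2.2 sets the primary rule: "Withdrawn subjects without the event will be censored at day of discontinuation (this assumes the censoring is non-informative"). SAP 12.5.2.1 rules out imputation for the primary estimand. SAP 10.11 and Protocol 9.3.2 censor in the same way.

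**Expected reasons for missing data.** SAP 12.5.3.1 gives three: discharged subjects who do not return, missed follow-up visits, "or a worsening of clinical status such that the subject can no longer participate in the trial". The section concerns the key secondary endpoints.

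**How deaths are found.** Protocol 8.3 collects survival at visits from Day 2 to Day 60. Protocol 7.1 keeps subjects who only stop the product in follow-up. Protocol 7.3 asks for telephone calls and, if necessary, a letter to the subject, and then: "Should the subject continue to be unreachable, he/she will be considered to have withdrawn from the trial". After participation ends, Protocol 8.5.1 puts no duty on the investigator to look for events. A serious event that becomes known, including a death, must be notified if "he/she considers the event to be reasonably related to the IMP or trial participation".

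**Sensitivity analyses.** SAP 10.19.2 imputes missing Day 60 status from arm, baseline score, pooled region, age and last known ordinal score. SAP 10.19.3 contains a mortality tipping point. Protocol 9.3.2 promises to investigate the impact of incomplete Day 60 follow-up.

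**Size.** Protocol 9.5 and SAP 8.1 describe the 50%-power limit: with 15 placebo deaths, "significance will be seen if at most 6 subjects die in the C21 group".

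**The concern.** Worsening is a strong pointer to death. If some subjects leave because they are deteriorating, those censored carry a higher risk than those who stay, and the assumption behind the primary test fails for them. They are the same subjects whichever section of the SAP describes them.

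The usual protection for a mortality endpoint is that death can be established without a visit. This plan does not use it. Survival is collected at visits, tracing is aimed at the subject, and the one rule on deaths that surface later turns on relatedness, which has no place in an endpoint of death from any cause.

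Incomplete Day 60 status is foreseeable here. Protocol 11 reports that all sites in Ukraine and Russia were closed, and Protocol 9.2 anticipates subjects lost for that reason. The same amendment made mortality the primary endpoint. The sections it lists as updated for the new endpoint (1.1, 3.0, 4.2, 9.1.1, 9.3.2 and 9.3.3) do not include 7.2, 7.3, 8.3 or 8.5.1, where follow-up and death reporting are set.

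With about 20 deaths expected in all, a few unrecorded ones can matter. Missed C21 deaths flatter the drug; missed placebo deaths hide a benefit.

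**Working it through.** **Inputs (Protocol 9.5, SAP 8.1).**
- 150 per arm: "With 150 evaluable subjects per trial group, there will be an 80% power to detect a difference".
- Two-sided 5% level: "This assumes using a 2-sided test at a 5% significance level".
- Placebo: "the proportion of subjects dead at Day 60 is estimated to 10"%, so 0.10 × 150 = 15 deaths.
- C21: 2.5%, so 0.025 × 150 = 3.75, about 4 deaths.
- Withdrawal 5%: 0.05 × 150 = 7.5, taken as 7 per arm.

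**Step 1: reproduce the plan's figures.** HR = ln(0.975)/ln(0.90) = 0.240, as stated. For the detection limit, use the Pearson test z = (p₁ − p₂)/√[p(1 − p)(2/150)], with p the pooled proportion. For 15 vs 6, p = 21/300 = 0.070, the standard error is 0.0295, z = 0.060/0.0295 = 2.04 and the p-value is 0.042. A simulated unstratified log-rank test with death times spread evenly over Days 1 to 60 also averages 0.042 (range 0.037 to 0.048). The stated limit reproduces. Simulated log-rank power is 80.0% without withdrawal and 78.7% with 5% withdrawal, close to the stated 80%.

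**Step 2: add deaths back.**

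| Placebo vs C21 deaths | p (chi-square) |
|---|---|
| 15 vs 4 (about the design expectation) | 0.009 |
| 15 vs 5 | 0.021 |
| 15 vs 6 (the plan's limit) | 0.042 |
| 15 vs 7 | 0.076 |
| 16 vs 7 | 0.051 |
| 14 vs 6 | 0.064 |

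- From 15 vs 6, one added C21 death loses significance. One added in each arm (16 vs 7) also loses it, narrowly.
- From 15 vs 4, three added C21 deaths are needed (15 vs 7), with none added to placebo.
- In the other direction, if the truth is 15 vs 6 and one placebo death goes unrecorded, the trial sees 14 vs 6 and p = 0.064.

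**Step 3: how likely is this?** The documents give no risk of death after withdrawal, so r is assumed: 5%, 10% or 20%, with 7 withdrawals per arm and independent outcomes.

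| Quantity | r = 5% | r = 10% | r = 20% |
|---|---|---|---|
| At least one unrecorded C21 death, 1 − (1 − r)⁷ | 30% | 52% | 79% |
| Observed 15 vs 4 loses significance, C21 deaths only (3 or more of 7) | 0.4% | 2.6% | 14.8% |
| Observed 15 vs 4 loses significance, same r in both arms | 0.4% | 2.2% | 9.5% |
| Observed 15 vs 6 loses significance, same r in both arms | 29% | 46% | 59% |

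The first row is the chance that a C21 death is hidden, not the chance that the result reverses.

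**Step 4: average over trials.** Simulating 1,500 trials per setting at 10% vs 2.5%, with 5% withdrawal and the same post-withdrawal risk in both arms, the censored analysis was significant where full follow-up was not in about 6% of trials at r = 10% and 10% at r = 20%.

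**The case against.** The strongest reply is that the plan discloses the assumption and tests it. Day 60 status is imputed using the last ordinal score, the variable most likely to carry the worsening. The mortality tipping point turns missing C21 survivors into deaths one at a time and runs exactly when the result is significant, so it should expose a one-death reversal. This stands, with limits. The imputation assumes data missing at random. Both analyses use a logistic risk difference, not the stratified log-rank test. The opening of SAP 10.19.3 names only key secondary endpoints, although a mortality subsection follows. And because the tipping point is skipped after a non-significant result, it cannot show a benefit hidden by missed placebo deaths.

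Follow-up is also not absent: Day 60 is a phone or video contact for discharged subjects, stopping the product does not end follow-up, and loss to follow-up is declared only after documented attempts. That should keep the number missing small. It does not reach subjects who leave the trial.

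Three stronger readings are tempting and are not supported.
- *Deaths after withdrawal are barred from the analysis.* They are not. SAP 12.5.2 censors subjects with no confirmed death, so a recorded death could count. The relatedness condition in Protocol 8.5.1 belongs to a safety-notification rule for post-trial events. The same section collects serious events until Day 60, and 8.5.3 follows open ones to an outcome or loss to follow-up, although 8.5.1 also ends adverse-event follow-up with participation. The gap is that nothing clearly requires such a death to be recorded.
- *Censoring at withdrawal contradicts the treatment-policy estimand.* The estimand text in Protocol 3 and SAP 12.5.2 itself specifies that censoring. The intercurrent events that SAP 12.5.2 lists concern stopping or changing treatment, not leaving the trial.
- *One missed C21 death overturns the trial at the expected counts.* 15 vs 6 is the 50%-power limit, not the expectation.

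**Conclusion.** The point holds as a gap in data collection for a mortality endpoint. The primary analysis relies on non-informative censoring, the SAP itself names a reason for dropout that would break it, and no section requires vital status after trial withdrawal. The planned sensitivity analyses describe the resulting uncertainty but do not remove it.

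The size depends on where the result lands. At 15 vs 6 a single unrecorded C21 death moves p from 0.042 to 0.076. At about 15 vs 4 it takes three, with no placebo death missed, and this is unlikely unless subjects who leave have a high risk of death. A reader might take the 30% to 79% figures as the chance of a reversed conclusion; that would be wrong except at exactly 15 vs 6 with no placebo death missed. The direction of bias cannot be known in advance.

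These figures rest on the plan's 5% withdrawal rate, assumed risks of death after withdrawal, 150 per arm, and unstratified tests in place of the stratified log-rank test. The change is worth making because it is cheap and protects the result in both directions; the plan is not invalid without it.

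**What to change.** - **Protocol 7.2, 7.3 and 8.3:** ascertain Day 60 vital status in the same way for every randomized subject, including those withdrawn or lost, from site or hospital records or a named contact, unless consent for this is withdrawn.
- **Protocol 8.5.1:** record any death up to Day 60 that the site learns of, whatever its relation to the product or the trial.
- **SAP 10.11 and 12.5.2.2:** count these deaths as events on their date; censor subjects confirmed alive at Day 60 at Day 60; for those whose status stays unknown, censor at the last date known alive.
- **SAP 10.19.2 and 10.19.3:** keep the imputation and tipping-point analyses for that remainder.

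The cost is protocol and consent wording and one vital-status field in the case report form. What can be obtained depends on local consent and privacy rules, and a few subjects will stay unknown.
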